**Number of subjects:**

Approximately 180 subjects will be enrolled in the study. Subjects will be randomly assigned to receive ALX-0171 dose 1, ALX-0171 dose 2, ALX-0171 dose 3 or placebo (N=45 per treatment group), yielding an overall allocation ratio of 3:1 active to placebo. Of these, 48 subjects (12 per dose group) will undergo more extensive PK sample analysis (3 PK samples per subject instead of 1 PK sample).

---

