#### *Rationale for Sample Size*

The sample size calculation is based on statistical considerations for the analysis of the primary endpoint. With 45 subjects per arm, 85% power is achieved to detect a 50% reduction in median time-to-BQL (0.5 day with ALX-0171 versus 1 day with placebo) for the plaque assay using a two-sided log-rank test at significance level of 0.05. For each comparison of the ALX-0171 dose groups with placebo, a significance level of 0.05 is assumed. For multiple pairwise comparisons, the family-wise error rate is controlled at 5% through the closed testing principle, where the comparison of the lower dose of ALX-0171 to placebo is only performed if the comparison of the higher dose of ALX-0171 to placebo is significant. The sample size calculation also assumes a drop-out rate of 15% to account for subjects dropping out prior to reaching the primary endpoint, or due to a false positive RSV test.

Change from baseline in Global Severity Score is a secondary endpoint of interest in this study. With this sample size, a power of 80% is achieved to detect a difference of 2 points

in the mean change from baseline (to Day 2 post-dose) on the Global Severity Score for each of the ALX-0171 dose groups to placebo. This is based on a two-sided t-test with a significance level of 0.05 and assuming a common standard deviation of 3.2 in each group.

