### 3.6.5. EVALUATION OF VIROLOGY AND CLINICAL EFFICACY ENDPOINTS

#### **3.6.5.1. ANALYSIS OF PRIMARY ENDPOINT**

For the primary endpoint, the anti-viral effect will be measured as the time-to-BQL in nasal mid-turbinate swab specimens. The median time-to-BQL will be compared between each of the ALX-0171 dose groups and the combined placebo group using a log-rank test. The tests will be performed in a sequential way to preserve the family-wise error rate at 0.05. Specifically, dose 3 of ALX-0171 will first be tested against the combined placebo group at the 0.05 significance level. Dose 2 of ALX-0171 will only be compared to placebo at the 0.05 significance level if the comparison of dose 3 with placebo is significant. Consequently, dose 1 of ALX-0171 will only be compared to placebo at the 0.05 significance level if the comparison of dose 2 of ALX-0171 with placebo is significant.

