## 4.2 Sample size

With 45 subjects per arm, 85% power is achieved to detect a 50% reduction in median time-to-BQL (0.5 day with ALX-0171 versus 1 day with placebo) for the plaque assay using a two-sided log-rank test at significance level of 0.05. For each comparison of the ALX-0171 treatment groups with placebo, a significance level of 0.05 is assumed. For multiple pairwise comparisons, the family-wise error rate is controlled at 5% through the closed testing principle, where the comparison of the lower dose of ALX-0171 to placebo is only performed if the comparison of the higher dose of ALX-0171 to placebo is significant. The sample size also incorporates a 15% drop-out rate. With this sample size, a power of 80% is achieved to detect a difference of 2 points in the mean change from baseline (to Day 2 post-dose) on the Global Severity Score for each of the ALX-0171 treatment groups to placebo. This is based on a two-sided t-test with a significance level of 0.05 and assuming a common standard deviation of 3.2 in each group.

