### 7.1 Primary Efficacy Endpoint Evaluation

The primary endpoint for this trial is the time needed for the viral load to drop below the plaque assay quantification limit (time-to-BQL) in nasal mid-turbinate swab specimens. Time to BQL is defined as the time from the reference point (first dosing) to the first occurrence of a value below the limit of quantification, provided the next measured value is below the limit as well. The time to event for subjects with missing data and/or who did not reach BQL during the trial will be censored at the last nonmissing viral load assessment .

The time-to-BQL will be compared between each of the ALX-0171 treatment groups and the combined placebo group using a log-rank test. The null hypothesis of this test assumes no difference in time-to-BQL between Placebo and ALX-0171 treated subjects. The tests will be performed in a sequential way to preserve the family-wise error rate at 0.05. Specifically, dose 3 (highest dose) of ALX-0171 will first be tested against the combined placebo group at the 0.05 significance level. Dose 2 of ALX-0171 will only be compared to placebo at the 0.05 significance level if the comparison of dose 3 with placebo is significant. Consequently, dose 1 of ALX-0171 will only be compared to placebo at the 0.05 significance level if the comparison of dose 2 of ALX-0171 with placebo is significant. The primary efficacy endpoint will be evaluated using the mITT population.

The logrank test is based on the assumptions that censoring is unrelated to prognosis and the event probabilities are the same for subjects recruited early and late in the study. Kaplan-Meier (KM) estimates on time-to-BQL will be tabulated (Median, 25th, 75th percentile with confidence interval and general information on censoring) and a graph of the Kaplan-Meier survival curve will be presented.

The data will also be analyzed using a Cox proportional hazards regression model with time to BQL as dependent variable, and treatment group, viral load at baseline and co-infected subject group as independent variables. The hazard ratio (HR) from the Cox model along with the 95% CI will be reported. This analysis will only be performed for the treatment groups where the comparison was significant as analyzed by the log rank test.

For sensitivity analyses, the primary endpoint will also be evaluated using:

- the RSV Infected population
- the Per Protocol population.

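### The log-rank test that decides each dose leaves out baseline viral load, a covariate the SAP itself selected; stratifying by it could add power at small cost

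*SAP*

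**What the plan says.** Protocol 3.6.5.1 names the primary test: "The median time-to-BQL will be compared between each of the ALX-0171 dose groups and the combined placebo group using a log-rank test". SAP 7.1 repeats it: "The time-to-BQL will be compared between each of the ALX-0171 treatment groups and the combined placebo group using a log-rank test". Neither gives a stratum or a covariate. Dose 3 is tested first. Dose 2 is tested only if dose 3 is significant, and dose 1 only if dose 2 is.

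SAP 7.1 then adds a Cox model with "treatment group, viral load at baseline and co-infected subject group as independent variables". The same paragraph restricts that model to doses already significant on the log-rank. The entry for Table 14.2.1.1 in SAP 16.2 lists the Cox output without that restriction, so the two places do not agree. SAP 7.1 also does not say which assay supplies the baseline viral load.

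Other relevant text:
- The protocol's Schedule of Assessments places a nasal swab before the Day 1 dose, and SAP 5.3.1 defines baseline as the last value before first dosing.
- Protocol 3.3.3 describes restricted randomization for the treatment arms and the PK substudy. It mentions no balancing on viral load.
- SAP 7.2.1 does adjust the key secondary endpoint, the Global Severity Score, for its own baseline.

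**The concern.** The endpoint is the time for a titre to cross a fixed limit. For a given rate of decline, an infant who starts higher takes longer to cross, whichever arm the infant is in. If that effect is appreciable, the arms are compared against a wide spread of crossing times that has nothing to do with treatment. An unadjusted log-rank then has less power than a test that uses the baseline value.

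The fixed sequence raises the stakes. If dose 3 misses significance, doses 2 and 1 are not formally tested, in a trial meant to support dose selection. The SAP's adjusted model cannot help, because under SAP 7.1 it is withheld from exactly those doses that miss on the log-rank.

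**Working it through.** **1. Inputs.** SAP 4.2: "With 45 subjects per arm, 85% power is achieved to detect a 50% reduction in median time-to-BQL", with medians of "0.5 day with ALX-0171 versus 1 day with placebo", "using a two-sided log-rank test at significance level of 0.05". Protocol 3.1.2: "The sample size calculation also assumes a drop-out rate of 15" percent. Evaluable infants per arm: 45 × 0.85 = 38.25, about 38. The documents do not state an event count. It is assumed here that every evaluable infant reaches BQL, giving 2 × 38.25 = 76.5 events per comparison.

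**2. The plan's own figure.** With exponential times, medians of 0.5 and 1 day give a hazard ratio of 2. The Schoenfeld formula gives events = 4 × (1.960 + 1.036)² / (ln 2)² = 74.7, so 75. Per arm that is 37.5 / 0.85 = 44.1, so 45. Power at 76.5 events is Φ(√76.5 × ln 2 / 2 − 1.960) = Φ(3.031 − 1.960) = 85.8%. The stated 85% reproduces. (Freedman's formula is slightly stricter: 81 events, 48 per arm, and 83.0% at 76.5 events.)

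**3. Model for the effect of baseline titre.** Let x be standardized baseline titre, x ~ N(0,1). An infant's rate of reaching BQL is λ × exp(ln 2 × arm − γx), where γ is the change in log hazard per SD of titre. λ is set so that the placebo median is 1 day. Treatment doubles every infant's rate, so the active median is 0.5 day at every γ. There are 38 infants per arm. Drop-outs are removed entirely, as uninformative loss. γ is an assumption, varied from 0 to 1.0 (hazard ratio per SD from 1.0 to 2.7).

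BQL can be seen only at swabs, so events were moved to the next of 5, 24, 29, 48 and 50 h, then 96 h (assumed discharge day) and 312 h (assumed follow-up, Day 13). Three two-sided 0.05 tests were compared: the unadjusted log-rank, a log-rank stratified at the median of x, and the treatment term of a Cox model containing x.

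**4. Power with events seen at swab times** (2,000 trials per setting, Monte Carlo error about 1 point)

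| γ | Log-rank | Stratified | Adjusted Cox | Change: stratified / Cox |
|---|---|---|---|---|
| 0 | 80.4% | 79.1% | 77.8% | −1.3 / −2.6 |
| 0.3 | 75.5% | 77.1% | 78.0% | +1.6 / +2.5 |
| 0.5 | 68.6% | 73.1% | 76.7% | +4.5 / +8.1 |
| 0.7 | 56.9% | 65.4% | 72.6% | +8.5 / +15.7 |
| 1.0 | 46.8% | 62.7% | 72.3% | +15.9 / +25.5 |

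A separate set of 500 trials per setting (error about 2 points) gave 78/76/75% at γ = 0, 76/79/78% at 0.3, 68/74/76% at 0.5 and 45/63/68% at 1.0. The changes are −2/−3, +3/+2, +6/+8 and +18/+23 points, which agree within simulation error.

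The fall from about 85% to about 80% at γ = 0 comes from seeing events only at swabs. It has nothing to do with adjustment.

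**5. Sensitivity to the set-up** (log-rank / stratified / Cox)
- Exactly observed times, medians still halved: 85/83/84% at γ = 0, 70/78/82% at 0.5, 48/63/82% at 1.0.
- Exactly observed times, treatment effect enlarged so that the log-rank itself has about 85% power: 86/85/86% at γ = 0.2, 86/86/88% at 0.3, 87/91/95% at 0.5, 86/93/98% at 0.7, 84/96/99.6% at 1.0.

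**6. Type I error at swab times** (3,000 null trials each, γ = 0.5 and 1.0). Log-rank 5.0% and 4.8%; stratified 4.9% and 4.8%; adjusted Cox 3.8% and 3.6%. None exceeds 5%.

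**The case against.** The strongest reply is that the log-rank is valid, prespecified, named in the protocol and correctly powered on its stated assumptions, so leaving it unadjusted is a defensible choice. No document gives a prognostic strength for baseline titre. With a weak covariate the gain is about nil. If the treatment effect is set so that the log-rank has its planned 85%, the Cox model gains only 0 to 2 points at γ of 0.2 to 0.3. Part of the loss in the table in step 4 of the working arises because the medians are held fixed while the spread of times grows. All of this stands, and it limits the size of the point.

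The reply also bears on the remedy. Replacing the log-rank with a Cox test would change the protocol's primary analysis, move to a conditional effect, and drop infants with no baseline titre. A pre-dose swab is scheduled for everyone, but items 57 and 58 of SAP Appendix C allow for missed and out-of-window swabs. The half-LLOQ rule in SAP 7.2.2.2 is for summary statistics and does not define a model covariate. These are reasons to keep the log-rank and stratify it.

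It can also be said that the SAP already contains an adjusted Cox model. That does not answer the point while SAP 7.1 runs the model only after a significant log-rank.

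A reader might infer that baseline titre is the main driver of this endpoint and that adjusting for it costs nothing. The documents do not say the first, and the row for γ = 0 contradicts the second.

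**Conclusion.** The point holds as a worthwhile efficiency improvement. The deciding test omits a pre-dose covariate that the SAP itself chose, and the only adjusted model is withheld where it would be most informative.

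With the plan's medians and events seen at swab times, adjustment changes power by about −3 to +3 points for γ between 0 and 0.3. It adds about 5 to 8 points at 0.5 and about 16 to 26 points at 1.0. Stratification gives the lower end of the last two ranges, and the adjusted Cox model gives the upper end. These sizes rest on the assumed γ, a normal covariate, proportional conditional hazards, uninformative drop-out and two assumed swab times. The simulation does not apply the SAP's requirement that the next value also be BQL.

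Two stronger readings are not supported. The 85% is not an error: it reproduces for the test as planned. Nor can one say that an adjusted Cox test would keep power above 80% whatever the prognostic strength. That pattern needs exactly observed times; at swab times the Cox figure is 72 to 78%.

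**What to change.** Before unblinding, in SAP 7.1:
- Keep the log-rank as the named test, but stratify it by baseline plaque titre, for example by a median split. Place BQL baselines in the low stratum and missing baselines in a stated stratum, so that every mITT infant is kept. Use the same dose 3, 2, 1 sequence at 0.05.
- Keep the unstratified log-rank as a sensitivity analysis.
- Report the adjusted Cox model for all doses whatever the log-rank result, which also brings SAP 7.1 into line with Table 14.2.1.1. State which assay supplies its baseline viral load and how ties are handled.
- Record the change in SAP 13, and as a change from protocol 3.6.5.1.

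No new data are needed. The cost is the wording, a documented departure from the protocol's primary analysis, and up to about 3 points of power if baseline titre is not prognostic.

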- e. For subjects who discontinue the study before Day 28, the Withdrawal visit will be conducted on the day of withdrawal as long as there has been no withdrawal of consent. If the Withdrawal visit assessments are performed within 6 hours after the Day 1, Day 2, Day 3, or in-hospital post-treatment Day assessments have been performed, the assessments already done at the prior time point do not need to be repeated and only the additional assessments to be performed on the Withdrawal Visit will need to be performed. No EOS visit needs to be performed after the Withdrawal Visit. In case subjects are hospitalized beyond the Day 14 FU visit, the additional assessments (in addition to the in-hospital post treatment period assessments) of the Day 14 FU visit need to be done on Day 14.
- f. RSV infection will be confirmed either according to routine site practice (PCR or diagnostic quick test), or using a (Sponsor-provided) commercial kit.
- g. Hospitalization information will include occurrence of ICU transfer, apnea episodes, initiation and type of ventilation and hospital/ICU discharge information. Assessment of Clinical Response will be done with collection of date and time of adequate oral feeding to enable discharge as well as adequate stable oxygen saturation on room air of  $>92\%$  over a period of at least 4 hours.
- h. Study drug will be administered via nebulization using the study-specific device. One dose consists of 2 serial nebulizations.
- i. A mid-turbinal nasal swab should be taken using provided kits and following specific instructions in case the subject is re-hospitalized or consults the Investigator for a respiratory condition after hospital discharge.
- j. A nasal swab should only be collected during the in-hospital post-treatment period on the day of hospital discharge.
- k. Physical examination includes examination of abdomen and skin and ears/nose/throat. Lung auscultation is listed separately as it is to be assessed more frequently.
- l. Continuous monitoring of SpO2 needs to be done until the clinical response criterion for oxygen has been met and/or in case saturation monitoring is to be continued according to the Investigator's judgment.
- m. Type of feeding support, if any, and feasibility of oral feeding.
- n. To assess wheezing, crackles/crepitation and other abnormalities in lung auscultation.

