## 13 CHANGE FROM ANALYSIS PLANNED IN PROTOCOL

Additional analysis on the primary endpoint was added using a Cox proportional hazards regression model with time to BQL as dependent variable, and treatment group, viral load at baseline and co-infected subject group as independent variables. These changes will not lead to an amendment of the clinical trial protocol

Following endpoints were added:

- Time between first study drug administration and discharge
- Duration of severe disease
- Duration of feeding support
- Subgroup analyses have been added for selected efficacy and safety endpoints

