## 16.2 Efficacy

**Table 14.2.1.1: Primary Endpoint: Time to below quantification limit of RSV viral load (plaque assay) (T)**

Kaplan-Meier analysis, including a two-sided Log-rank test. The output will include number of events, number of censored values, median, 25% percentile and 75% percentile of time to event with 95% CIs and p-value of the log-rank test. Additionally the results of a Cox proportional hazards regression model with time to BQL as dependent variable, and treatment group, viral load at baseline and co-infected subject group as independent variables will be reported including Hazard ratio (95% CI) and p-value

Population: mITT population.

**Table 14.2.1.2: Sensitivity analysis - Time to below quantification limit of RSV viral load (plaque assay)-RSV Infected population (T)**

Kaplan-Meier analysis, including a two-sided Log-rank test. The output will include number of events, number of censored values, median, 25% percentile and 75% percentile of time to event with 95% CIs and p-value of the log-rank test. Additionally the results of a Cox proportional hazards regression model with time to BQL as dependent variable, and treatment group, viral load at baseline and co-infected subject group as independent variables will be reported including Hazard ratio (95% CI) and p-value

Population: RSV infected population.

**Table 14.2.1.3: Sensitivity analysis - Time to below quantification limit of RSV viral load (plaque assay)-Per Protocol analysis (T)**

Kaplan-Meier analysis, including a two-sided Log-rank test. The output will include number of events, number of censored values, median, 25% percentile and 75% percentile of time to event with 95% CIs and p-value of the log-rank test. Additionally the results of a Cox proportional hazards regression model with time to BQL as dependent variable, and treatment group, viral load at baseline and co-infected subject group as independent variables will be reported including Hazard ratio (95% CI) and p-value

Population: Per Protocol population.

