**Listing 16.2.3.8: Viral Load**

Listing per subject and time point of RSV viral load (plaque assay and RT-qPCR), including time to BQL and time weighted average change from baseline. Population flag for RSV infected population will be included

Population: mITT population

**Listing 16.2.3.9: Time to Clinical response - Adequate oxygen saturation and oral feeding - Product limit survival estimates**

Listing of product limit survival estimates from the corresponding Kaplan Meier analysis

Population: mITT population

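### The Cox hazard ratio is planned only for doses with a significant log-rank test, so the HRs that appear are exaggerated on average and some or all doses may have none

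*SAP*

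**What the plan says.** SAP 7.1 compares each dose with the combined placebo group by log-rank test in a fixed sequence. Dose 3 comes first, dose 2 is tested only if dose 3 is significant, and dose 1 only if dose 2 is. It then plans a Cox model with treatment group, baseline viral load and co-infection status, reporting the HR with a 95% CI, under this condition: "This analysis will only be performed for the treatment groups where the comparison was significant as analyzed by the log rank test".

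The same section says "Kaplan-Meier (KM) estimates on time-to-BQL will be tabulated" (median and quartiles with confidence intervals, and a curve), with no such condition. In SAP 16.2, the descriptions of Tables 14.2.1.1 to 14.2.1.3 (mITT, RSV Infected and Per Protocol) state that the Cox results "will be reported including Hazard ratio (95% CI) and p-value", again without the condition. SAP 13 records the model as a change from the protocol: "Additional analysis on the primary endpoint was added using a Cox proportional hazards regression model". It does not mention the restriction there either.

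**The concern.** An estimate that is shown only when its own test reaches p<0.05 is a selected estimate. Results that happen to be small are dropped, so the average of those that survive lies too far from 1. The smaller a real effect is, the stronger the exaggeration. The fixed sequence adds a second problem: a dose can lose its HR because a higher dose missed significance.

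Nothing else planned fills the gap. The Kaplan-Meier quartiles describe each arm separately, and the log-rank test gives only a p-value. Protocol 3.1.2 says the study is meant to support choice of the optimal dose, so HRs that are inflated to different degrees, or absent, are a poor basis for comparing doses. When a test fails, the HR with its interval is what separates little effect from little information, and that is what the rule withholds.

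**Working it through.** **Inputs.** From SAP 4.2: 45 per arm, 85% power, two-sided 0.05, medians 0.5 versus 1 day; also "The sample size also incorporates a 15% drop-out rate". With exponential times (an assumption), halving the median gives HR 2.0 for reaching BQL. HRs of 1.5 and 1.3 are illustrative and not in the documents.

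**Reproducing the design.** Schoenfeld events = 4(1.96 + 1.036)²/(ln 2)² = 74.7, so 75. That is 38 per arm, and 38/0.85 = 44.7, so 45. With 76 events the power is 85.6%. The plan's figures are reproduced. (Freedman's formula gives 81 events and 49 per arm, so it is not the one used.)

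**Selection effect, normal approximation.** SE of the log HR = 2/√76 = 0.229. An unadjusted HR must reach exp(1.96 × 0.229) = 1.57 to be significant. Let m = ln(HR)/0.229 and P = 1 − Φ(1.96 − m). The mean log HR given significance in favour of active is 0.229 × [m + φ(1.96 − m)/P]. For HR 1.5: m = 1.77, P = 0.424, and 0.2294 × (1.767 + 0.3916/0.4236) = 0.617, so the mean reported HR is 1.85. For these three HRs, CI coverage among reported results is (P − 0.025)/P.

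| True HR | P(reported) | Mean reported HR | CI coverage when reported |
|---|---|---|---|
| 2.0 | 85.6% | 2.13 | 97% |
| 1.5 | 42.4% | 1.85 | 94% |
| 1.3 | 20.7% | 1.78 | 88% |

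**Missing HRs under the fixed sequence** (2,000,000 draws, correlation 0.5 from the shared placebo arm). If all true HRs are 2.0, an HR is shown for doses 3/2/1 in 86/77/70% of trials; none is shown in 14%, and at least one is missing in 30%. If all are 1.5, the figures are 42/26/19%, 58% and 82%.

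**Simulation closer to the plan.** Four arms of 45 with a shared placebo, exponential times with placebo median 1 day, 15% drop-out, selection by the unadjusted log-rank test in sequence, and a Cox HR adjusted for one covariate (log HR 0 or 0.5 per SD, assumed). Event times were either exact (about 76 events per comparison) or read at swabs at 5, 22, 29, 46 and 50 h and Day 14. In the second case BQL had to be confirmed, since 7.1 counts a value only "provided the next measured value is below the limit as well"; this gave 66 to 73 events. The post-treatment swab was left out because its time is not fixed: "A nasal swab should only be collected during the in-hospital post-treatment period on the day of hospital discharge". There were 4,000 trials per setting (8,000 for the graded case). Dose 3 geometric mean HRs over the four settings:

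| True HR | All trials | Significant, favourable trials | CI coverage when reported |
|---|---|---|---|
| 2.0 | 1.93–2.07 | 2.15–2.28 | 96–99% |
| 1.5 | 1.48–1.54 | 1.89–1.93 | 90–95% |
| 1.3 | 1.29–1.32 | 1.80–1.85 | 85–88% |

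No dose has an HR in 15 to 31% of trials at 2.0 and in 57 to 70% at 1.5. With true HRs of 2.0/1.5/1.3 for doses 3/2/1, taking the simulation and the normal approximation together, an HR is shown in 69–86% / 27–41% / 9–16% of trials, averaging 2.1–2.3 / 1.9 / 1.8–1.9. Selection uses the unadjusted test while the HR is adjusted, so there is no hard floor at 1.57: 1–3%, 2–11% and 2–17% of reported HRs fall below it at true 2.0, 1.5 and 1.3.

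**Second simulation.** 38 per arm, 30% co-infection, covariate log hazard 0 or −0.3 per SD, 3,000 trials per setting. The mean over all trials is 2.07 at true 2.0 and 1.52–1.53 at true 1.5. Among significant trials it is 2.23–2.25 and 1.93–1.95. Removing the restriction therefore removes the bias from selection.

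**The case against.** The Cox model is supplementary. The protocol's primary analysis is the log-rank test alone, and neither that test nor the error rate is touched. At the only effect size in the documents, HR 2.0, the exaggeration is small (2.13 against 2.0, about 6%) and coverage among reported intervals stays near nominal. The larger distortions rest on illustrative HRs. Dose selection can draw on many outputs that carry no significance condition: Kaplan-Meier summaries, proportions BQL, viral load over time, and the pairwise GSS contrasts. Subject-level data are also kept: "Listing per subject and time point of RSV viral load (plaque assay and RT-qPCR), including time to BQL". All of this stands and limits the weight of the point.

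Two further points are fair. First, the bias arises only if 7.1 prevails over the unconditional table descriptions. The inconsistency between the two is certain; the bias depends on how it is resolved. Second, at a true HR of exactly 1 the two-sided condition leaves the signed average log HR at 0, although an HR that is significant in favour of active then averages about 1.71.

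None of this defends the rule. An HR derived later from listings is not a pre-specified result. The multiplicity argument does not apply, because an estimate with an interval and a descriptive p-value makes no confirmatory claim.

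**Conclusion.** The point holds and should be corrected, although it is not critical. The restriction is explicit, nothing in the SAP withdraws it, and it makes the only planned between-arm estimate on the primary endpoint conditional on significance. The distortion is modest at the design effect and substantial below it. In the graded example, true HRs of 1.5 and 1.3 would, when shown, both appear at about 1.8 to 1.9, so the difference between the two lower doses is nearly lost.

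The figures assume exponential times, the event counts given above and the stated covariate effects. The chance of no HR for any dose is 1 minus the power for dose 3, so it moves with those assumptions. The direction of the bias for a non-null effect does not depend on them.

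**What to change.** Delete the restricting sentence in SAP 7.1. Report the Cox HR with 95% CI for all three doses versus placebo, whatever the log-rank result, in the mITT, RSV Infected and Per Protocol populations. Keep the fixed sequence for the confirmatory log-rank p-values only, and label the Cox p-values descriptive.

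The cost is one sentence deleted and one label, which should also be carried into the three table descriptions in SAP 16.2 because they list a bare p-value. Those descriptions then agree with 7.1 on when the HR is shown. The deletion also settles a question 7.1 leaves open: whether the condition in the two sensitivity populations refers to the mITT log-rank result or to each population's own. The primary test, the sample size and the family-wise error rate do not change.
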